Accessible Chiropractic Care and an Integrated Multidisciplinary Chronic Pain Team: Observational Study of Strategies to Manage Chronic Spinal Pain and Reduce Prescription Opioids in a Federally Qualified Health Center

Date: July 1, 2018

Background

Chronic spinal pain is one of the most common complaints encountered in the United States health system (16-18). One multi-center study determined that 31% of primary care visits in community settings involved chronic lower back or neck pain (18). Furthermore, the annual prevalence of nonspecific neck pain in a Canadian study was estimated to be between 30 and 50% (26); the global point prevalence of low back pain (LBP) is estimated at around 9%, with an estimated 80% lifetime prevalence (9, 10). Out of all 291 conditions studied in the Global Burden of Disease 2010 Study, LBP ranked highest in terms of disability (years lived with disability), and sixth in terms of disability adjusted life-years (DALYs) (9). In addition to the effect on patients, LBP costs the medical system an estimated \$260 billion annually, not including indirect costs of lower household productivity and days of work lost (6,7).

The treatment of chronic spinal pain often involves a stepwise approach that includes non-steroidal anti-inflammatories (NSAIDs), rest, exercise, physical therapy, and sometimes prescription opioids (11, 26). Unfortunately, opioid analgesics have failed to demonstrate long-term efficacy in managing chronic pain, at the cost of numerous adverse effects, including addiction and overdose (3). Now at the forefront of public health challenges, opioid-related deaths have quadrupled from 1999-2015, with 33,091 deaths attributed to opioid overdoses in 2015 (11, 12).

As a response, there have been multiple efforts to study the effects of non-pharmacologic treatments for chronic spinal pain. Patients seeking these modalities have been shown to have higher satisfaction with their management and lower costs to the health system (14, 16, 19). Chiropractic physicians manage patients with chronic spinal pain using non-pharmacologic therapies, namely spinal and soft tissue manipulation, work/activity modification, and exercise and lifestyle advice. Chiropractic care is a clinically-proven safe and effective strategy for managing spinal pain resulting in lower pain scores and increased patient satisfaction with minimal adverse events (16, 20, 21, 24). In a recent systematic review, chiropractic care was equally effective as physical therapy, but there is only limited evidence of equality with medical care (23).

Low-income patients might be underrepresented in chiropractic clinics. Although there have been numerous cited attempts to include underserved patients in chiropractic care, there are few studies reporting efficacy of such programs. One Canadian study demonstrated that an urban chiropractic clinic could achieve sustainability and effectively reduce spinal pain (25). Furthermore, on-site chiropractic care in the workplace has been proven to reduce overall

healthcare utilization, including emergency department visits, outpatient visits, and radiologic images (13). Although no such study known to these authors has been published integrating chiropractic care within a federally qualified health center (FQHC), it can be hypothesized that this model would improve patient outcomes and satisfaction, while reducing healthcare costs and potentially reducing opioid prescriptions.

Affinia Healthcare is a multi-site FQHC in St. Louis, Missouri serving more than 40,000 patients per year. Recently, this organization has developed two unique strategies to manage chronic pain: 1) a multidisciplinary pain team and 2) chiropractic care. In 2016, Logan University College of Chiropractic began partnering with FQHCs, including Affinia Healthcare, whereby chiropractic providers treat patients within these medical homes. Using a flat rate of \$10 USD per visit, this enhances access to chiropractic care for its low-income population. One goal of this study will be to examine the effectiveness of chiropractic care in a low-income urban population within a FQHC.

There have been a few studies reporting the use of integrated multidisciplinary pain teams in primary care, which have endorsed this model for its acceptability, affordability, and feasibility among the primary care team members (1,2,4,5). These have focused on qualitative outcomes, and did not focus on endpoints of opioid dose reduction or reduction in patient pain scores. In order to assess the effectiveness of the integrated pain team, this study will investigate pain and disability score reductions and opioid weaning success.

In order to best assess both pain and functional status, this study will use the Pain Disability Questionnaire (PDQ) as its validated quantitative assessment tool. As opposed to traditional pain scales, it incorporates both psychosocial and functional status components; because of this it is a useful survey to assess the impact of interventions to reduce pain and improve function, including chronic spinal pain (27, 28).

References

3. Kuehn BM. AHRQ: Little evidence for opioids in managing long-term chronic pain. *JAMA*. 2014;312(12):1185. <http://dx.doi.org/10.1001/jama.2014.12752>. doi: 10.1001/jama.2014.12752.

4. The integrated pain team: A mixed-methods evaluation of the impact of an embedded interdisciplinary pain care intervention on primary care team satisfaction, confidence, and perceptions of care effectiveness. .
5. Those conversations in my experience don't go well": A qualitative study of primary care provider experiences tapering long-term opioid medications. .

- b. Control group: For this proposed pilot study, there will be no control group. Ideally, a standard care group could be analyzed, but currently, Affinia does not have the administrative or IT support to incorporate the PDQ in its workflow or medical records. Future studies could be designed and planned with this in mind if the initial studies have impactful results.

c. *Inclusion/exclusion criteria.*

Inclusion criteria: Individuals with chronic (>90 days) spinal pain at Affinia healthcare that have been referred internally to either chiropractic care or the integrated multidisciplinary pain team.

Exclusion criteria: Patients deemed to have non-mechanical spinal pain from malignancy, compression fracture, or inflammatory spondyloarthropathy.

- d. The target number of enrolled patients per treatment is 30. Thus approximately 60 patients will be enrolled. Enrollment period is estimated to be three months, and will end when the target participant number is achieved. Patients will be followed a total of 6 months. Data analysis may take an additional 3 months. Thus this study will take approximately 12 months.
- e. Data will be stored both electronically and paper-format. A hardcopy of the Patient Disability Questionnaire (PDQ) will be provided. This hardcopy will be used to help guide clinical decisions during the visit, and then scanned into the electronic health record (EHR). Medications, including opioid prescriptions, will be recorded in the EHR. A list of enrolled patients will be kept in Microsoft Excel.
- f. Enrolled participants will be tracked in a Microsoft Excel spreadsheet to be stored in Affinia Healthcare's user-specific and password-protected desktop computers with drive encryption. In order to track opioid prescriptions, the enrolled patient list can be exported to Affinia's IT department to run a medication search. This information will be relayed to the study team to enter in the database. Any discrepancies, suspected to be minimal, will require a manual chart review. This will be done by someone other than the investigators such as the IT data analyst so as to minimize bias. Prior to final data analysis, data will be de-identified. All data transactions will be done through secure, encrypted server e-mail.
- g. *Will the data set include any sensitive information (e.g., HIV status, psychiatric diagnosis)?* No.
- h. *Will the data set include any genomic data?* No.
- i. *Will your data be used in collaborative efforts with other institutions?* Yes. [name], DC, DACBR and [name], DC, MHA, DIBCN, will be co-investigator from Logan University. The faculty of Logan University who have patient privileges at Affinia Healthcare have access to the same EHR and servers, and data will remain in the same secure, encrypted locations.

3. Study Statistics

Primary outcome variable:

- i. Difference in PDQ (functional and psychosocial scores)
- ii. Proportion of patients weaned from opioids by the end of study period

Secondary outcome variables:

- i. Odds of treatment success by demographic factor (age, sex, origin, other musculoskeletal pain diagnoses, etc.)
- ii. Proportion of patients successfully reduced on morphine equivalent dose (any reduction)
- iii. Proportion of eligible patients who adhere to treatment (show rates)

Analysis plan (sample size justification and interim analysis)

Sample size calculations will be technically challenging due to the observational nature of the dual-intervention study design. We will estimate that standard care results in 90% failure rate to positively change PDQ scores or wean opioids. We will estimate the true relative risk of treatment failure is 0.5. Using the null hypothesis that there is no difference between the treatments and that there is no difference between either treatment and standard care, our calculations predict that 16 experimental subjects will be needed per intervention. The proportion of cross-over patients is unknown, so a conservative 50% will be used, and thus 32 (30 for ease of estimation) patients will be needed per group to reject the null ($\alpha=0.05$, power=0.8). We will use the chi-squared statistic to evaluate this null hypothesis. Two-sample t-test and multiple linear regression will be conducted to determine the demographic and clinical features associated with outcomes. Most demographic factors will be binary or categorical, including age.

Variables to collect

- i. Age (categorical)
- ii. Sex
- iii. Preferred language
- iv. Country of origin
- v. Insurance (categorical)
- vi. Type of spinal pain (cervical, lumbar)
- vii. Morphine equivalent dose
- viii. Other musculoskeletal pain diagnoses (hip pain, shoulder pain, etc.)

4. Risks

- a. *Address the risk of loss of confidentiality.*
- b. *Discuss the steps you are taking to minimize this risk.*
- c. *Discuss your plan for reporting unanticipated problems or study deviations*

There are no anticipated medical, legal, or financial risks to the participants. There is no randomization and no placebo. Patients will be studied as part of a treatment plan dictated independently by their medical providers. Risks to confidentiality will be minimized by the following procedures: study records will be accessible only to authorized study staff, and the generated data report for analysis will be de-identified.

Chart reviews will be conducted for enrolled study participants, gathering pre-selected variables.

This study relies upon a steady referral stream to Affinia chiropractic care and the pain team. Currently, these are accessible and well-utilized services, but there is no way to predict the future trend of these referrals. Any unanticipated change in providers, access to the pain team or chiropractic services, or patients refusing participation will extend the enrollment period.

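### The implied success/failure outcome sets no minimum PDQ change and lets either PDQ improvement or weaning count, so noise alone can pass as success and weaned-but-worse patients are not visible

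*Combined protocol and SAP*

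**What the plan says.** Section 3 (Study Statistics) lists two primary outcomes: the difference in PDQ, covering functional and psychosocial scores, and "Proportion of patients weaned from opioids by the end of study period". The primary objectives in section 1 match them: PDQ change over time, and the proportion weaned.

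The analysis plan in section 3 then works with one binary quantity. It assumes: "We will estimate that standard care results in 90% failure rate to positively change PDQ scores or wean opioids". It continues: "We will estimate the true relative risk of treatment failure is 0.5". From these it concludes that "our calculations predict that 16 experimental subjects will be needed per intervention", doubles that to 32 for an assumed 50% cross-over, and rounds to 30. The null hypothesis has two parts: no difference between the two interventions, and no difference between either intervention and standard care. The test is named: "We will use the chi-squared statistic to evaluate this null hypothesis".

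Treatment success also appears in the secondary objectives and secondary outcomes, as the dependent variable for the demographic factors. Neither success nor failure is defined anywhere. There is no PDQ cut-off and no statement of whether the two components are combined. Section 2b says there is no control group. Section 2c does not require opioid use at baseline.

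**The concern.** Two features of the implied outcome matter.

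First, a positive PDQ change of any size qualifies. A score that moves by chance in the favourable direction makes the patient a success. With no control group, chance movement cannot be subtracted by comparison with untreated patients. The reference is an assumed 90% failure rate, so a responder proportion made up largely of noise could be read as a large treatment effect.

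Second, on the natural reading either event is enough. A patient who weans while the PDQ deteriorates is a success. If the two parts are instead meant as separate outcomes, that patient still counts fully towards the weaning proportion, which carries no PDQ condition. The Background says of the pain team that "this study will investigate pain and disability score reductions and opioid weaning success", and section 1 sets the goal of reducing both pain and opioid use. Yet no planned output shows whether the patients who weaned are the ones who improved or the ones who worsened.

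**Working it through.** **1. The plan's own figure.** Inputs from section 3: failure 0.90 under standard care, relative risk 0.5, alpha 0.05 (two-sided assumed, since the plan does not say), power 0.80. Treated failure is 0.90 × 0.5 = 0.45, and the average of the two rates is 0.675. With pooled variance and no continuity correction:

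n = [1.960 × √(2 × 0.675 × 0.325) + 0.842 × √(0.90 × 0.10 + 0.45 × 0.55)]² / (0.90 − 0.45)² = (1.298 + 0.489)² / 0.2025 = 15.8, so 16 per group.

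Then 16 / (1 − 0.5) = 32. Both figures reproduce. Power is 80.6% at 16 per group and 97.8% at 30 with no cross-over loss. The arithmetic is sound; the question is what the binary outcome measures.

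**2. Failure rate with no PDQ effect.** Assume PDQ changes are symmetric about zero with no ties, and that weaning is independent of PDQ movement. Half of patients then move favourably by chance, and failure = 0.5 × (1 − proportion weaned). The documents give no weaning rate, so a range is shown.

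| Proportion of all patients weaned (assumed) | Failure with no true PDQ effect |
|---|---|
| 0% | 50% |
| 10% | 45% |
| 20% | 40% |
| 30% | 35% |

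**3. What the comparison with 90% would then show.** The plan does not say how a chi-squared test against standard care is run without a control group. The simplest version treats 90% as a fixed known rate. With 30 patients and a true rate of 0.90, P(22 or fewer failures) = 0.008 and P(23 or fewer) = 0.026. A lower-tail limit of 0.025 therefore rejects at 22 or fewer. If the true failure rate is 50%, with no PDQ effect and no weaning, P(22 or fewer) = 0.997. If the plan's 50% cross-over left 15 patients, the limit would be 10 or fewer (P = 0.013 under 0.90; 11 or fewer gives 0.056), and P(10 or fewer) at 50% failure is 0.941.

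This concerns only the standard-care half of the null. Noise of the same size in both interventions would not by itself produce a difference between them.

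**4. Where each type of patient appears, on the natural reading.**

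| Patient | Binary outcome | Weaning proportion | PDQ difference |
|---|---|---|---|
| Weaned, PDQ worse | Success | Weaned | Enters the average with its sign |
| Not weaned, PDQ worse | Failure | Not weaned | Enters the average with its sign |
| Not weaned, PDQ unchanged | Failure | Not weaned | Contributes zero |
| Not weaned, PDQ trivially better | Success | Not weaned | Enters the average with its sign |

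No column identifies the first row as a group.

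**5. What a stricter definition costs.** Suppose a share s of intervention successes is reclassified as failure, with standard care kept at 0.90. Treated failure becomes 1 − 0.55 × (1 − s). The values of s are assumptions.

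| s | Treated failure | n per group (before cross-over inflation) | Power at 30 per group |
|---|---|---|---|
| 10% | 0.505 | 20 | 93.8% |
| 20% | 0.56 | 26 | 86.2% |
| 30% | 0.615 | 35 | 74.3% |
| 50% | 0.725 | 77 | 40.9% |

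If the same share is also removed from standard-care successes, n is 19, 23, 27 and 42.

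**The case against.** The strongest reply is that the quoted sentence is a planning assumption, not an endpoint definition. Its *or* may mean 90% failure on each outcome separately, and the outcomes are in fact listed separately. This stands as a limit on the point: the plan states no operational rule. The fault is that success and failure are left undefined while carrying the sample size, the chi-squared test and the analysis of demographic factors.

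A reader might go further and infer that harm from weaning is reported as benefit. The documents do not support that. The PDQ difference is a primary outcome in its own right and keeps its sign, so average worsening would appear. Classing worsening with no change occurs only inside the binary outcome, where both are failures. What is hidden is narrower: individual patients who wean and worsen. No count can be given for them, because the documents contain no rate of worsening after weaning, and patients not on opioids at baseline cannot wean.

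A second reply is that 90% failure under standard care is hard to square with a rule that about half of unchanged patients pass by chance, so the authors may have meant more than trivial movement. That is fair, but it does not remove the problem. Either a threshold was intended and is missing, or the 90% does not fit the outcome as worded.

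It is also tempting to note that 10% weaning with no PDQ effect gives exactly the plan's 45%. That match depends on the weaning rate chosen and proves nothing; the range of 35% to 50% is the result.

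**Conclusion.** The point holds as a gap in outcome definition with a real consequence for inference. With symmetric noise, no ties and no true PDQ effect, failure would be about 50%, or 35% to 40% if 20% to 30% of all patients wean independently. Against a fixed 90%, 30 patients would give rejection with probability above 99%. The planned comparison with standard care could therefore reject the null with no real PDQ benefit. This rests on reading any favourable movement as success and on treating the 90% as the reference, since the plan supplies neither a threshold nor a control group.

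Separately, no planned output links weaning to PDQ change, so patients who wean and worsen would not be visible. Their number is unknown. It does not follow that weaning should count only when the PDQ is not worse. Weaning is a stated primary objective in itself, and a not-worse rule without a margin would reclassify about half of weaned patients with no true PDQ change by chance.

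**What to change.** In section 3:

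- **(a)** Define a PDQ responder as a favourable change larger than a pre-set measurement-error threshold, and state the threshold's source. The PDQ papers already cited (references 27 and 28) are the natural place to look, though whether they supply one cannot be checked from the documents. Make the 90% and 45% failure assumptions consistent with this definition.
- **(b)** Keep PDQ change and weaning as separate primary outcomes. For each intervention, among patients on opioids at baseline, report weaned/not weaned by PDQ improved, unchanged or worsened, using the same threshold.
- **(c)** Report the proportion of all patients whose PDQ worsens beyond the threshold.

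The data are already to be captured (section 2, items e and f), so the work is protocol wording, one extra table and one extra proportion. The success proportion will be lower, and so will power for the binary comparison: about 74% at 30 per group if 30% of intervention successes are reclassified and standard care stays at 90%. If the assumed rates change, the stated power and sample size should be restated before analysis.

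### One unadjusted alpha of 0.05 covers a three-part null and two primary outcomes; 5% holds only for one overall test on a composite that the outcome list does not define

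*Combined protocol and SAP*

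**What the plan says.** All of this is in section 3 (Study Statistics) unless noted.

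- **Null.** The analysis plan works from "Using the null hypothesis that there is no difference between the treatments and that there is no difference between either treatment and standard care". That is chiropractic care v pain team, and each of the two v standard care.
- **Primary outcomes.** There are two list items: "Difference in PDQ (functional and psychosocial scores" (i) and "Proportion of patients weaned from opioids by the end of study period" (ii). Section 1 also lists PDQ change and weaning as separate primary objectives.
- **Error rate.** Alpha appears once, with the final size of 32 (taken as 30): "patients will be needed per group to reject the null ($\alpha=0.05$, power=0.8".
- **Test.** "We will use the chi-squared statistic to evaluate this null hypothesis". The plan does not say whether this is one overall test or a set of pairwise tests.
- **Planning rates.** "We will estimate that standard care results in 90% failure rate to positively change PDQ scores or wean opioids" and "We will estimate the true relative risk of treatment failure is 0.5".
- **Control group.** Section 2, item b says there is none, so standard care enters only as the assumed 90%.

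The document gives no hierarchy, split of alpha, multiplicity adjustment or correlation between outcomes.

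**The concern.** A stated alpha of 0.05 tells the reader that, if neither service does anything, the study has a 5% chance of a positive primary result. That requires one identified primary test. Here three comparisons and two outcomes, one of them with two scores, share the 0.05, and the plan does not say which combination it belongs to. The choice could then be made after the results are known.

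The consequence is practical. The stated goal is to determine the effectiveness of the two interventions, and section 2, item b makes a future controlled study depend on how persuasive these results are. A false positive on one of several unranked tests could be read as the study's primary finding.

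**Working it through.** **1. Reproduce the plan's figure.** Inputs from section 3: failure p1 = 0.90; relative risk 0.5, so p2 = 0.45; alpha 0.05; power 0.80. The plan does not state sidedness. The mean is p̄ = 0.675.

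n = [z(1−α/2)·√(2p̄(1−p̄)) + z(0.80)·√(p1(1−p1) + p2(1−p2))]² / (p1 − p2)²

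Here √(2 × 0.675 × 0.325) = 0.6624, √(0.09 + 0.2475) = 0.5809 and (p1 − p2)² = 0.2025.

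n = (1.960 × 0.6624 + 0.8416 × 0.5809)² / 0.2025 = (1.298 + 0.489)² / 0.2025 = 15.8, so 16.

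This matches "our calculations predict that 16 experimental subjects will be needed per intervention". Then 16 / 0.5 = 32 for the cross-over allowance, rounded in the plan to 30. The other variants tried do not give 16: one-sided 13 (17 with continuity correction), two-sided with correction 20, arcsine 15, unpooled variance 14. The size therefore rests on a single two-sided 0.05 test.

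**2. Count the possible primary tests.** Three comparisons on two outcomes make six tests. If the functional and psychosocial scores are tested separately, there are three outcome variables and nine tests.

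**3. Chance of at least one false primary finding, each test at two-sided 0.05, no true effect anywhere.** For each service and outcome, draw a standard normal statistic Z. The test against a fixed benchmark uses Z_A or Z_B; service v service uses (Z_A − Z_B)/√2; reject if the absolute value exceeds 1.96. Groups are equal in size. The correlations are assumptions: 0 to 0.8 between the two PDQ scores, and 0 to 0.6 between PDQ and weaning. One million draws per row.

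| Outcomes tested | Assumed correlation | Service v service only | All three comparisons |
|---|---|---|---|
| One composite | none needed | 5.0% | 11.5% |
| One PDQ score, weaning | 0 | 9.8% | 21.7% |
| One PDQ score, weaning | 0.3 | 9.5% | 21.1% |
| One PDQ score, weaning | 0.6 | 8.7% | 19.5% |
| Two PDQ scores, weaning | all 0 | 14.2% | 30.6% |
| Two PDQ scores, weaning | PDQ 0.8, weaning 0.3 | 12.2% | 26.2% |
| Two PDQ scores, weaning | PDQ 0.8, weaning 0.6 | 11.1% | 24.0% |

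Across the separate-outcome rows this is about 9% to 14% for service v service, and roughly 19% to 31% for all three comparisons. If one PDQ score and weaning were correlated at 0.8, the two-outcome figures would fall further, to 7.8% and 17.4%.

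**4. One overall chi-squared test instead of pairwise tests.** On one composite it gives 5%. Run separately on two independent outcomes it gives 1 − 0.95² = 9.8%; on three, 1 − 0.95³ = 14.3%.

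**5. Size at a stricter level, same formula.**
- Alpha 0.025: (2.241 × 0.6624 + 0.489)² / 0.2025 = 19.2, so 20; after the 50% allowance, 40.
- Alpha 0.0125: (2.498 × 0.6624 + 0.489)² / 0.2025 = 22.7, so 23; after the allowance, 46.

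With 30 enrolled per group and the plan's 50% allowance, 15 remain. Power on the same formula is then 78% at 0.05, 67% at 0.025 and 56% at 0.0125.

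**The case against.** The plan speaks of one statistic for one null, and the sentence on the 90% rate can be read as a single failure outcome combining PDQ and weaning. One overall test on that outcome has a 5% error rate. There is also no control group, and no standard-care value is given for a PDQ score or for weaning alone, so separate tests of those outcomes against standard care cannot be run as the plan stands. Primary objective i speaks of one PDQ score, so the two named scores may only describe the questionnaire's components. The study calls itself a pilot and is not randomised, so strict family-wise control carries less weight.

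Much of this stands. A reader might infer that the type I error simply is 21% to 31%, or about one in four. The documents do not support that. It requires pairwise tests, outcomes tested separately, both standard-care comparisons carried out, and low outcome correlation, and the plan commits to none of these. The 37% from nine independent tests (1 − 0.95⁹) is further off, because the tests share groups.

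The normal approximation also has limits for small binary groups. An uncorrected chi-squared test of two groups of 15 to 16 at 90% failure has a true size of about 2.5% to 2.8%.

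The objection does not remove the gap. The composite appears only in the planning assumption, while the primary outcomes are two separate items. A single overall rejection would not say which service differs. Dropping the standard-care comparisons still leaves about 9% to 14%. A pilot that states a null, alpha and power should say what the alpha covers.

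**Conclusion.** The point holds in conditional form. The plan states no multiplicity control, its size allows for one test, and 5% is delivered only by one overall test on a composite that the primary outcome list does not contain. With the primary outcomes tested separately, the error is about 9% to 14% for service v service, and roughly 19% to 31% if all three comparisons are made on each outcome against a fixed benchmark. One composite over three pairwise comparisons gives 11.5%.

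These figures assume no true effect, equal groups, normal test statistics and the correlations given above, none of which come from the documents. No single figure can be called the plan's error rate until the primary test is named. The gap affects how the primary result is read; it does not invalidate the study.

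**What to change.** In section 3:

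1. Name one PDQ score for primary outcome i, and state the comparison and outcome to which alpha = 0.05 applies.
2. Label the remaining scores, the other comparisons and the subgroup receiving both services as exploratory, reported with 95% confidence intervals and no significance claim.
3. If PDQ and weaning both stay primary, either control the two with Holm (first step 0.025) or restate 0.05 as a per-comparison level with the family-wise figure beside it.
4. Describe any test against standard care as a test against an assumed fixed benchmark, and give its value for the outcome concerned, because there is no control group.

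The change is to wording and needs no new data. Its cost is a stricter threshold if alpha is divided: on the plan's own formula, 16 becomes 20 at 0.025, or 23 at 0.0125 if four tests were kept as primary, before the cross-over allowance. Restate the power for the planned 30 per group rather than enrol more. Naming a single primary test, or restating 0.05 as per-comparison, leaves the stated size unchanged.

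### The PDQ is a numeric primary outcome, but the only stated hypothesis test is chi-squared on a yes/no composite, and no stated analysis compares the two services on the score

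*Combined protocol and SAP*

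**What the plan says.** The Background chooses the instrument for being numeric: "this study will use the Pain Disability Questionnaire (PDQ) as its validated quantitative assessment tool". Section 1 makes change in PDQ score over time the first primary objective, and section 3 gives primary outcome i as "Difference in PDQ (functional and psychosocial scores").

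The analysis plan in section 3 then works on a different scale. The sample size starts from a failure proportion: "We will estimate that standard care results in 90% failure rate to positively change PDQ scores or wean opioids". It adds an effect on that proportion: "We will estimate the true relative risk of treatment failure is 0.5". The null hypothesis covers both the contrast between the two services and the contrast of each service with standard care. The test is then named: "We will use the chi-squared statistic to evaluate this null hypothesis".

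The next sentence names a two-sample t-test and multiple linear regression, but for identifying demographic and clinical features related to outcome. It mentions no term for service. No SD, expected mean change, distribution or responder cut-off for the PDQ appears anywhere. Section 2b states that there is no control group, and section 2d sets the target at 30 patients per treatment.

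**The concern.** The first primary outcome and the only stated hypothesis test do not match. The outcome is a score; the test sees only failed or not failed, and merges the score with a second outcome, weaning, that is already yes/no. A patient whose PDQ improves by one point and a patient whose PDQ improves greatly count the same.

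This matters because the study is small. It has 30 patients per service, and its own 50% cross-over allowance would leave 30 × (1 − 0.5) = 15. With those numbers, a between-service difference that the collected scores could show may be missed, and the result would carry no mean difference or interval in PDQ points. Section 2b looks ahead to later controlled studies; a mean change with its SD is what their design would need, and a failure rate does not supply it.

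**Working it through.** **1. The plan's own figure.** Inputs from section 3: standard-care failure 0.90; relative risk 0.5, so treated failure 0.45; alpha 0.05 (taken as two-sided); power 0.80. The pooled formula for two proportions, without continuity correction, gives

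n = [1.96 × √(2 × 0.675 × 0.325) + 0.8416 × √(0.90 × 0.10 + 0.45 × 0.55)]² / 0.45² = (1.298 + 0.489)² / 0.2025 = 15.8, so 16.

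This matches: "our calculations predict that 16 experimental subjects will be needed per intervention". Dividing by (1 − 0.5) gives 32, which the plan rounds to 30. The calculation is therefore wholly about a yes/no endpoint.

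**2. Information kept by a yes/no cut.** Assume PDQ change is normal with the same SD in both services. The large-sample efficiency of a cut that leaves proportion p on one side is φ(z)² / [p(1 − p)].

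- p = 0.5: 0.3989² / 0.25 = 0.637.
- p = 0.9 (z = 1.2816): 0.1755² / 0.09 = 0.342.

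So about 36% to 66% of the information is lost over that range of cuts.

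**3. What that means between the services.** The plan states no between-service effect, so take 0.75 SD as an illustration, with 30 v 30 and two-sided 5%.

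- *Score.* The t-test has noncentrality 0.75 × √(30/2) = 2.905 on 58 df, giving power 0.81.
- *Yes/no, reference failure 50%.* The other service has Φ(0 − 0.75) = 0.227. Power = Φ{[0.273 × √30 − 1.96 × √(2 × 0.363 × 0.637)] / √(0.250 + 0.175)} = Φ(0.252) = 0.60.
- *Yes/no, reference failure 45%.* The other service has Φ(−0.126 − 0.75) = 0.191. The same formula gives 0.58.
- *Yes/no, cut midway between the two means.* Failure is Φ(0.375) = 0.646 v 0.354. The formula gives 0.62 and exact enumeration of the uncorrected test gives 0.64.

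The yes/no test therefore has power of roughly 0.58 to 0.63, against 0.81 on the score. Put as the smallest difference detectable with 80% power, the score needs 0.74 SD at 30 v 30 and the yes/no test 0.97 to 0.99 SD (reference failure 50% or 45%). At 15 v 15 the figures are 1.06 SD and 1.44 to 1.54 SD.

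**4. Sensitivity to the assumption.** These are simulations of the same 0.75 SD shift at 30 v 30.

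- *Unequal SDs, normal, cut at the reference median.* The score does better at SD ratios from 0.75 to 2 (at 1.25, 0.71 v 0.43). The yes/no test does better at 0.5.
- *Heavy tails (Laplace), central cut.* Chi-squared has power 0.91 and the t-test 0.81 to 0.82, so the ordering reverses.

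**The case against.** The strongest objection is that the size of the loss is not a fact about this study. The documents give no PDQ distribution, and step 4 shows that the advantage of the score can vanish or reverse. That stands. The percentages in step 2 belong to the normal, equal-SD model, and the 0.75 SD effect is chosen for illustration.

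A reader might go further and turn the plan's 90% v 45% into a PDQ shift: z(0.90) − z(0.45) = 1.2816 + 0.1257 = 1.41 SD. At 15 per group this gives power of 0.96 for a t-test and 0.81 for chi-squared (exact, uncorrected), which suggests that the plan loses that much at its own effect. The documents do not support this, for four reasons.

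- The rate is a composite with weaning, so it cannot all be assigned to the PDQ.
- It contrasts treatment with standard care, and no standard-care group is enrolled.
- At the 30 per group in section 2d, the same model gives about 0.98 against above 0.99, a negligible gap.
- The result depends on the SDs: at 16 per group, with the treated SD twice the other, t-test power is 0.76, below the 0.81 that the formula gives for chi-squared.

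A reader might also infer that the services will never be compared on the PDQ score. The text does not say that. A service term in the regression is unspecified but not excluded.

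Finally, a between-service contrast does not by itself estimate change within each service, which is primary objective i. Analysing two PDQ scores plus weaning also raises multiplicity. Both are fair, but the present list of primary outcomes already raises them, and neither is a reason to test the PDQ only as yes/no.

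**Conclusion.** The point holds in a limited form, as a change that should be made. What rests on the text alone is that a numeric primary outcome has no stated between-service analysis as a number, and that the only hypothesis test named uses a yes/no composite with no PDQ cut-off given.

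The size is conditional. If PDQ change is roughly normal with similar SDs, the cut keeps about a third to two thirds of the information, and a moderate-to-large difference of 0.75 SD at full enrolment goes from power of about 0.81 to roughly 0.58 to 0.63. With heavy tails or very unequal SDs the gain is smaller or reversed. No power loss should be quoted at the plan's 90% v 45%.

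**What to change.** In section 3:

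- Analyse PDQ change as a score, for the functional and psychosocial components, by the linear regression already planned, with a term for service. Report mean differences with 95% confidence intervals. Use the t-test, in its unequal-variance form, as the simple version.
- State how patients who use both services enter the model: either as their own category or only in the subgroup analysis that section 2a already plans.
- Keep chi-squared for the proportion weaned, and show the proportion improved on the PDQ descriptively.
- State that the 16-per-group calculation refers to the yes/no composite against an assumed standard-care rate, and so does not give the power of the PDQ score comparison.

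The cost is wording: no new data, patients or software. The small downsides are that the main PDQ result is in points rather than a success rate, and that the sample-size paragraph must be reworded to match.
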